## 4. Introduction and Background

Our primary hypothesis is that the bubble-enhanced or BEFAST exam will be more sensitive than traditional FAST for identification of solid organ injury in hemodynamically stable blunt abdominal trauma patients when performed by emergency providers. The purpose of this study is to ascertain whether the BEFAST exam is a more sensitive screening tool than traditional FAST exam. BEFAST addresses a major limitation of conventional FAST in that it can identify lacerations to solid organs even in the absence of hemoperitoneum. Acceptance of the BEFAST exam as an appropriate alternative to CT in select situations may positively impact patient care by leading to decreased CT utilization and a change to current trauma algorithms.

Blunt abdominal trauma - whether from motor vehicle crash, assault, fall, or recreational injury - is a leading cause of morbidity and mortality [1]. According to the 2016 National Trauma Database, 12 % of all patients with trauma admissions had abdominal trauma, the majority of which is blunt [2]. The diagnosis of intra-abdominal injury due to blunt abdominal trauma can be challenging. The physical exam is unreliable in patients with altered mental status or with impairment due to drugs or alcohol. Utilization of the FAST exam has dramatically improved clinical care by enabling frontline providers to screen for injury non-invasively.

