# 11. Incidental Findings

The research team will relay any findings related to injury to solid organs and hemoperitoneum to the primary treatment team for further management. The FAST and BEFAST exams are screening exams only and not comprehensive abdominal exams; additional findings are not anticipated. If additional incidental findings are noted they will be relayed to primary treatment team for appropriate triage, referral to clinical specialists, and patient education as needed if the finding is clinically significant. All study patients will also obtain confirmatory imaging with CT study.

12. Compensation for time and effort: \$25 single payment as reimbursement for parking expenses, time, effort.

13. Statistical Analysis:

**Objective 1**: To determine if contrast-enhanced, i.e. bubble-enhanced FAST (BEFAST) outperforms non-enhanced FAST in the evaluation of solid organ injury in hemodynamically stable blunt abdominal trauma patients when performed by frontline providers using CT as gold-standard.

Descriptive Statistics. The primary results will be described using sensitivities and specificities with 95% confidence intervals. Categorical variables will be described using frequencies and percentages. Continuous variables will be described using means and/or medians as appropriate.

Primary Analyses. Agreement with the CT results will be examined using a mixedeffects/multi-level logistic regression in order to account for clustered measurements. Results from this regression will also be adjusted for the following covariates: demographics (e.g. age, sex, race), BMI, sonographer experience, contrast redosing, the presence of outward signs of injury. In the event that the logistic regression fails to estimate properly or provides poor fit to the data and/or to show consistent results across methods, alternative methods will be explored: (1) P-values and confidence intervals will be computed using a bias-corrected and accelerated bootstrapping procedure ( $\geq$ 5,000 resamples); (2) Sensitivities and specificities for BEFAST and FAST will be compared using McNemar's test.

Sample Size Calculations. Two primary issues were taken into consideration when calculating the required sample size: 1) statistical power, and 2) the expected rate of positive outcomes.

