1) Power calculations were based on previous studies examining the sensitivity and specificity on standard and contrast-enhanced ultrasound. The results from these studies were meta-analyzed (fixed-effects, inverse-variance method) and indicated that (1) the sensitivity for CEUS (lower limit = 0.87) is greater than the sensitivity for standard ultrasound (upper limit = 0.68); and (2) the specificity for CEUS (0.98) is similar to the specificity for standard ultrasound (0.95). This analysis aimed to ensure that the present study has sufficient power to show improved sensitivity when using CEUS. Note that, because this sample size calculation uses the lower limit of the CEUS estimate and the upper limit of the standard ultrasound estimate, actual power will likely be greater. Given the small meta-analytic difference in specificities between methods, it is unlikely that differences in specificity will be detected. These values were used to estimate the sample size required to achieve 80% power using Monte Carlo simulations (10,000 samples) implemented in R v3.4.1. This analysis determined that the sample size would need to be at least 187.

2) Using the rule of thumb 10 positive results for each predictor, we aimed to ensure that there will be a sufficient number of positive results for a model with two predictors (i.e. at least 20 positives. Thus, the current study will aim for a sample size of at least 187; however, data collection will not end until at least 20 CT+ patients are enrolled. Importantly, this stopping rule is entirely a priori and ceasing data collection will not be dependent on any statistical analyses, significance tests, or interim analyses. No analyses will be conducted until after this stopping rule is reached.

Missing Data. In the event of substantial missing data, data will be imputed using a multiple imputation procedure. The type of procedure and the number of imputed data sets will be determined by the amount of missing data and the pattern of missingness. As a sensitivity analysis, we will 1) assume the worst and assign a "does not agree" outcome for that patient and 2) assume the best and assign an "agrees" outcome for that patient. These analyses will describe the boundary conditions for the models described above.

**Objective 2**: To determine whether emergency physicians can incorporate BEFAST evaluation at the point-of-care in a trauma evaluation of a hemodynamically stable adult blunt abdominal trauma patient.

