An exam is complete if the patient tolerates the exam (no severe adverse reaction to contrast, patient allows the provider to complete the scan) and if it results in images of adequate quality to answer the focused clinical question.

Completion rates will be described as percentages with 95% confidence intervals. Assuming maximal variance for a binomial variable ( $\pi = 0.5$ ), a sample size of 187-267 (approximate) will result in 95% CIs that are no wider than  $\pm$  7.2% to 6.0%. FAST and BEFAST completion rates will be compared using either the multilevel/mixed effects logistic regression described above or McNemar's test.

**Objective 3**: To determine the interrater reliability between bedside emergency physicians and radiologists for identifying solid organ injury with BEFAST.

Inter-rater Reliability for the presence/absence of an injury will be evaluated using Cohen's or Fleiss' kappa as appropriate. The reliability of AAST scores will be evaluated using a weighted kappa statistic.

Assuming a minimal sample size of 187, the current study will have sufficient power ( $\geq$  80%) to detect reliability coefficients exceeding 0.23. For clinically relevant ratings, such as this, reliability is generally required to be high. Guidelines vary and are generally arbitrary; however, 0.8 and 0.9 are often used as cutoffs for "high" agreement, whereas a value such as 0.23 would be considered unacceptable. Thus, the current study is sufficiently powered to detect clinically acceptable levels of agreement.

14. Data and Safety Monitoring and Reporting:

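### The hypothesis and power target are sensitivity, but the named primary analysis models agreement with CT and designates no sensitivity contrast

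*Combined protocol and SAP*

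**What the plan says.** Section 4 states as the primary hypothesis that the "BEFAST exam will be more sensitive than traditional FAST for identification of solid organ injury". The Sample Size Calculations in section 13 have the same target: "This analysis aimed to ensure that the present study has sufficient power to show improved sensitivity when using CEUS".

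Under Objective 1 in section 13, the Primary Analyses paragraph names a different outcome: "Agreement with the CT results will be examined using a mixedeffects/multi-level logistic regression", used "in order to account for clustered measurements" and adjusted for covariates. It gives no model equation, no restriction to CT-positive patients, no exam-by-CT-status interaction and no primary contrast. Alternative methods apply if the regression "fails to estimate properly or provides poor fit to the data and/or to show consistent results across methods". The second alternative is the only formal test of sensitivity in the plan: "Sensitivities and specificities for BEFAST and FAST will be compared using" McNemar's test.

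Under Descriptive Statistics, "The primary results will be described using sensitivities and specificities with 95% confidence intervals". This covers each exam's estimates and does not name a difference between the exams.

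**The concern.** Overall agreement with CT mixes sensitivity and specificity, weighted by the share of CT-positive patients. At the shares plausible here, most of the weight falls on CT-negative patients. If the exam effect in the primary model pools both groups, it does not test the hypothesis in section 4.

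The main harm is misattribution: a specificity gain alone could make the primary test significant and be reported as support for higher sensitivity. A second, conditional harm is lost power for a real sensitivity gain. It arises if specificity does not improve and the two exams are not strongly nested.

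**Working it through.** **Does the text imply a pooled model?** This is an inference, because no equation is given. Three places point to it:
- The model is there to handle clustering.
- The Missing Data paragraph codes each patient's outcome as agreeing or not agreeing, without limiting this to CT-positive patients.
- Under Objective 2, FAST and BEFAST completion rates are to be "compared using either the multilevel/mixed effects logistic regression described above or" McNemar's test, which implies exam type as the predictor.

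One place leaves doubt. Sample-size item 2 counts CT-positive patients for a two-predictor model. That could mean a CT-positive-only model, or CT status regressed on both exams.

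**Inputs**
- Sensitivity 0.68 (FAST) and 0.87 (BEFAST), specificity 0.95 and 0.98: section 13, sample-size item 1.
- N = 187 (section 13) and 267 (section 6).
- Share CT-positive, *p*: no expected value is stated. Range used: 10.7% (20/187, a stopping floor rather than a prevalence estimate) to 20% (the upper bound for intra-abdominal injury in section 4).
- Alpha and sidedness are not stated; two-sided 5% is assumed.
- Within-patient dependence is not stated. Correlation 0 to 0.3 within CT stratum is used, with fully nested exams as the upper bound (maximum correlation 0.56 for 0.68/0.87 and 0.62 for 0.95/0.98).

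**Step 1: the plan's 187.** It has no unique reproduction, because alpha, *p*, dependence and the simulated test are not given. The paired McNemar sample size at 80% power, with discordant probabilities *a* and *b* and *d* = *a* − *b*, is

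n = [1.96√(a+b) + 0.8416√(a+b−d²)]² / d².

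For sensitivity with independent reads, a = 0.87×0.32 = 0.2784, b = 0.68×0.13 = 0.0884 and d = 0.19. This gives n = 77.4, so 78 CT-positive patients. With nested reads, a = 0.19 and b = 0 give 39. Dividing by *p*, the totals are 390 and 195 at 20%, and 729 and 365 at 10.7%. Totals near 187 arise from either target: 191 for sensitivity with independent reads at *p* = 41%, and 192 for agreement with intermediate dependence at *p* = 20%. The figure therefore does not show which test was simulated.

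**Step 2: what agreement measures.** Agreement = p×Se + (1−p)×Sp.
- p = 0.107: FAST 0.0728 + 0.8484 = 0.921; BEFAST 0.0931 + 0.8751 = 0.968. Of the 0.0471 gain, 0.107×0.19 = 0.0203 (43%) comes from sensitivity.
- p = 0.20: 0.896 versus 0.958. Of the 0.062 gain, 0.038 (61%) comes from sensitivity.

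The specificity loss that would cancel a 19-point sensitivity gain is 0.19p/(1−p), which is 2.3 points at 10.7% and 4.75 points at 20%.

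**Step 3: paired simulation.** 100,000 replicates, one binary result per patient per exam, McNemar standing in for the mixed model. Entries are the percentage of trials significantly favouring BEFAST over *p* = 10.7–20%: asymptotic test, with the exact test in brackets where available.

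| Scenario | N | Agreement, corr. 0–0.3 | CT-positive only, corr. 0–0.3 | Agreement, nested | CT-positive only, nested |
|---|---|---|---|---|---|
| (a) Se 0.68/0.68, Sp 0.95/0.98 | 187 | 14.5–25.2 (9.8–18.3) | 2.2–2.6 (0.6–1.5) | 66.0–74.0 (29.4–38.8) | 0 |
| (a) | 267 | 17.7–36.2 (13.9–27.6) | 2.2–2.7 | 88.6–93.0 (62.1–72.1) | 0 |
| (b) Se 0.68/0.87, Sp 0.95/0.95 | 187 | 12.6–36.5 (8.2–27.7) | 27.1–63.0 (16.2–51.7) | 52.5–92.7 (18.1–71.7) | same |
| (b) | 267 | 15.3–48.4 (11.2–39.4) | 37.3–79.9 (27.8–72.6) | 79.3–99.2 (46.1–94.2) | same |
| (c) Se 0.68/0.87, Sp 0.95/0.98 | 187 | 55.0–83.1 (45.4–76.6) | 27.0–62.6 (15.9–51.1) | 97.9–99.8 | 52.9–92.9 |
| (c) | 267 | 71.2–94.5 | 37.0–79.8 | 99.9–100 | 79.4–99.2 |

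In (a) nested at N=187, only about 0.03×(1−p)×187 = 4.5 to 5.0 discordant pairs are expected. That explains the wide gap between the asymptotic and exact results.

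**Step 4: would a CT-status main effect help?** A marginal logistic model with patient-clustered standard errors was run for scenario (a) at N=187 (6,000 replicates, correlation 0–0.3). It favours BEFAST in 13.0–24.1% of trials with exam only, and in 14.0–26.6% with exam plus a CT-status main effect. Without the interaction, the misattribution remains.

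**The case against.** The pooled reading rests largely on silence. Clustering and agree/disagree coding also fit a CT-positive-only model, in which agreeing is the same as testing positive. The rule on the number of CT-positive patients, and the remark that a specificity difference is unlikely to be detected, suggest that the authors thought of sensitivity separately. McNemar on sensitivities is already named, and sensitivities with intervals will be reported, so a reader could see that no gain had occurred. Objective 1 asks the broader question of whether BEFAST performs better, which overall agreement could answer. Scenario (a) departs from the planning values, and on those values the agreement test has more power. The largest figures depend on the asymptotic test with few discordant pairs.

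Much of this is fair. The reading is an inference, the power loss is conditional, and the exact figures belong beside the asymptotic ones. If the model is organ-level, these simulations do not apply directly. But if several models fit the text, the primary test is still not fixed, and on none of these readings does the plan designate a sensitivity contrast as primary. Intervals for each exam are not a test of the paired difference. The extra power of agreement comes from a specificity gain that the sample-size text itself sets aside, so it is not power for the stated hypothesis.

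**Conclusion.** The concern holds and should be fixed; confidence is medium because the model is not written out. The hypothesis and power target are sensitivity, while the designated primary analysis is agreement with CT.

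On the pooled reading, with no sensitivity gain and a 3-point specificity gain, the primary test would favour BEFAST in roughly 10–25% of trials at N=187 and 14–36% at N=267, taking the exact and asymptotic tests together at correlation 0–0.3. The rates are higher if the exams are nested. Such a result would be a correct finding about accuracy but would not support the sensitivity hypothesis. These sizes rest on the assumed alpha, CT-positive share and dependence, and on unadjusted stand-ins for the covariate-adjusted mixed model. The mismatch itself rests on the text alone.

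**What to change.** Write out the primary model and name its primary contrast. Make the paired BEFAST–FAST comparison of test positivity in CT-positive patients the primary test. This can be McNemar's test, or a mixed model for test positivity with exam, CT status and their interaction, taking the exam effect at CT-positive as primary. Report the CT-negative contrast as the specificity result and move overall agreement to secondary. Restate power for that test, giving the assumed CT-positive share, paired dependence, alpha, sidedness and test.

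The cost is SAP wording and a new power paragraph; the change of contrast needs no new data. Section 13 bars analyses until the stopping rule is met, so up to that point the change can be made without sight of results.

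The downside should be stated openly. For 0.68 versus 0.87 at 10.7–20% CT-positive and correlation 0–0.3, the CT-positive-only test has about 27–63% power at N=187 (exact 16–52%) and 37–80% at N=267 (exact 28–73%). If the exams are nested, it reaches up to 93% (exact 72%) and 99% (exact 94%). By the Step 1 formula, 80% power would need 195 to 729 patients in total across these assumptions. The restated paragraph should therefore say whether 187 or 267 is still considered adequate.

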While the FAST exam is considered a first line tool in the triage of hemodynamically unstable patients with abdominal trauma to CT scanner versus the OR, its inability to identify lacerations to the solid organs in the absence of hemoperitoneum limits its utility in the hemodynamically stable patient. A 2018 Cochran review noted substantial heterogeneity of reported sensitivity of the FAST exam; pooling results from 34 studies it estimated FAST sensitivity for abdominal trauma to be 68% and specificity to be 95% [3]. Most studies use free fluid as the only criteria for a positive FAST exam. When FAST is used to detect solid organ injury it is less sensitive; both McGahan et al and Rothlin et al. showed a sensitivity of 41% for the ability of FAST to detect solid organ injury [4-6]. In comparison, gold standard CT has a sensitivity of 97-98% and specificity of 97-99% for intra-abdominal injury [7]. The use of the BEFAST exam may bridge this diagnostic gap between FAST and CT if it can demonstrate improved sensitivity in detecting lacerations to liver, kidney, spleen, and pancreas.

While CT can rapidly and accurately diagnose injury, emergency physicians have raised concerns that the use of CT has become overly liberal [8]. Over the last few decades there has been a paradigm shift in the management of solid organ trauma with increasingly nonoperative management of both low and high-grade injuries in hemodynamically stable patients [9-10]. 25% of all CTs are ordered through the ED, but less than 20% of abdominal CTs obtained in patients with blunt trauma have intra-abdominal injury, and less than 3% require a surgical intervention [7].

The risks of overutilization of CT in hemodynamically stable blunt abdominal trauma include increased health care costs, lengthy stays in the emergency department, risks of contrast-induced nephropathy and radiation-induced malignancy, and patient anxiety when "incidentalomas" are discovered that need extensive and often unnecessary workup

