# 6. Study Design and Methods:

This single center prospective study will enroll 267 adult patients with hemodynamically stable blunt abdominal trauma who present to a Level 1 ACS verified Trauma Center.

Inclusion Criteria: Age 18 and older Clinical suspicion of intra-abdominal injury Presentation within 24 hours of injury Planned CT of the abdomen/pelvis within 24 hours Ability of patient to provide informed consent

Exclusion Criteria: Co-existing penetrating abdominal injury Known hypersensitivity reaction to contrast agent Pregnant patients Prisoners No appropriate IV Line able to be inserted Hemodynamic instability at time of enrollment (sustained systolic blood pressure < 90 mm Hg or sustained HR >120 despite initial resuscitation) Study Interventions/Procedures:

1) Baseline Grayscale US Exam

2) Contrast Enhanced US exam with IV administration of LUMASON

3) Chart Review for abstraction of clinical and demographic data

Risks/discomforts:

Risks from ultrasound use are minimal – this modality does not use ionizing radiation. Most commonly the patient may complain of coldness of gel or minor discomfort from pressure of the ultrasound probe.

The less common risks and discomforts expected in this study are (in 0.02% of patients):

Headache, nausea, dizziness, flushing, back pain, kidney pain, chest pain, shortness of breath, hypertension, mild allergic reactions

Rare but possible risks include: hypersensitivity to contrast resulting in low blood pressure (0.007% of patients).

Potential benefits include: identification of injuries with BEFAST not seen with conventional FAST

Ultrasound studies will be performed by a team of ultrasound faculty who have attended a didactic session on the BEFAST exam and grading of solid organ injury by AAST criteria. They will be evaluated with a post-test to check for comprehension.

After consent, a baseline FAST exam will be performed and documented. This FAST will be distinct from the initial ATLS resuscitation FAST in order to avoid any interference in the trauma evaluation. A 20g or larger intravenous line if not already placed, will be established according to standard practice for trauma patients. The investigator will use a phased array or curvilinear transducer to record video of their baseline FAST exam. The investigator will also note start/stop time of the FAST exam.

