Using the same machine, a BEFAST exam will be performed using a low mechanical index setting in contrast-specific imaging mode. Lumason will be injected into the patient's IV for the CEUS exam by either a nurse research coordinator or one of the clinical staff. The contrast will be injected using the straight port of a 3-way stopcock and flushed through the side port. To eliminate shear of microbubbles, contrast will not be injected through a clave connector. The contrast will be injected once for the right side of the body, and once for the left side of the body looking for disruptions in the normal enhancement pattern and evidence of active bleeding. If an antecubital line is placed, 2.4 mL contrast will be given over slow IV push (2-3 seconds) and flushed with 5 ml saline; if only a peripheral hand IV is established, the investigator may use a 10 ml saline flush.

To examine the right side of the body: the right kidney and liver will be imaged. The investigator will examine the RUQ for evidence of solid organ injury, free fluid, or active extravasation by examining the kidney in short and long views and the liver in coronal, anterior, and subcostal views.

The examiner will screen the liver during approximately the first 10-20 seconds after IV contrast administration to see hypoperfusion in the arterial phase or extravasation before scanning through all organs in the venous phase (kidney, then back to liver). The exam will be timed from start of saline flush after contrast and video clips will be saved (stored using patient study number).

To examine the left side of the body: the pancreas will be imaged first, followed by the kidney and the spleen. The investigator will note evidence of solid organ injury, free fluid, or active extravasation in the LUQ. The pancreas, kidney, and spleen will be visualized in short and long. The exam will be timed from start of saline flush after contrast and video clips will be saved. If adrenal glands are visualized on either side these may be recorded as well.

In general, the investigator will scan one side of body at time but may cross to the other side if imaging on one side is complete. Investigators will be allowed to re-dose contrast on either or both sides if the first examination is not clear or if there is inadequate time to complete the exam. Either right side or left side may be examined first.

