The investigator will note the presence or absence of injury to the liver, kidney, spleen, or pancreas, as well as the presence or absence of free fluid or active extravasation. If an injury to a solid organ is detected, the investigator will grade injury per American Association for the Surgery of Trauma (AAST) criteria. There will be an attestation noting whether there was unintended disclosure of either the primary team's FAST exam or CT imaging read prior to bedside interpretation of the BEFAST study. The investigator will note whether there were physical exam signs suggestive of injury that may have biased their interpretation. The investigator will note start/stop time of BEFAST exam. Exams will be saved to QPATH and to the US machine; the data will also be archived on an encrypted USB. QPATH will be password protected, and the USB will be kept in a locked file in a locked office. The US machine will be kept in a locked file in a locked office.

A study is complete if the patient tolerates the study (no severe adverse event to contrast, patient allows the provider to complete the scan) and if it results in images of adequate quality to answer the focused clinical question.

A serious adverse event (SAE) is defined by the FDA as any adverse drug event (experience) occurring at any dose that in the opinion of either the investigator or sponsor results in any of the following outcomes: 1) death 2) life-threatening adverse drug experience 3) inpatient hospitalization or prolongation of existing hospitalization (for > 24 hours) 4) persistent or significant incapacity or substantial disruption of the ability to conduct normal life functions 5) congenital anomaly/birth defect 6) important medical event (IME) that may not result in death, be life threatening, or require hospitalization may be considered a serious adverse drug experience when, based upon medical judgment, it may jeopardize the patient or subject and may require medical or surgical intervention to prevent one of the outcomes listed in this definition.

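### Contrast redosing, which can happen only during BEFAST, is an adjustment covariate in the FAST–BEFAST agreement regression; coded as it occurs, it turns the adjusted contrast into non-redosed BEFAST versus FAST

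*Combined protocol and SAP*

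**What the plan says.** Section 13, Objective 1, makes a mixed-effects logistic regression of agreement with CT the primary analysis, to allow for clustered measurements. It continues: "Results from this regression will also be adjusted for the following covariates", and the list reads "covariates: demographics (e.g. age, sex, race), BMI, sonographer experience, contrast redosing, the presence of outward signs of injury". The plan does not say how redosing is coded, adds no interaction or standardisation step, and does not say which coefficient is the primary estimate.

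Under Descriptive Statistics the same section says: "The primary results will be described using sensitivities and specificities with 95% confidence intervals". McNemar's test and a bootstrap are named as alternatives, for use if the regression fails or fits poorly, or to show consistency.

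Section 6 fixes the order of the exams. After consent "a baseline FAST exam will be performed and documented"; this is a grayscale exam without contrast. BEFAST follows, and in it investigators may "re-dose contrast on either or both sides if the first examination is not clear or if there is inadequate time to complete the exam".

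**The concern.** Age, sex, race and BMI belong to the patient and are settled before either exam. Redosing is different: it is an event inside one of the two tests being compared, and it is triggered by how that test is going. FAST cannot be redosed.

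Objective 1 asks whether BEFAST, delivered with redosing allowed, outperforms FAST. A model that holds redosing fixed can answer another question: how BEFAST compares with FAST when no second dose is given. If redosed scans are the difficult ones, that removes the difficult BEFAST scans from the contrast while keeping every FAST scan. At stake is the meaning of the adjusted exam-type odds ratio and the width of its confidence interval.

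**Working it through.** The plan gives no figure for redosing, so there is none to reproduce. The check has an algebraic part, which needs no data, and an illustrative part.

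**1. What the coefficient means.** Write logit P(agree) = a + b·BEFAST + c·redosed + patient effect.
- Redosing coded as it occurs (0 on every FAST row): b is non-redosed BEFAST versus FAST, and b + c is redosed BEFAST versus FAST. Centring redosing leaves b unchanged.
- Redosing coded per patient (same value on both rows): c cancels from the within-patient contrast, and b stays with BEFAST as performed.

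**2. Inputs.**
- Accuracy, from Sample Size Calculations item 1: sensitivity 0.68 (FAST) and 0.87 (BEFAST); specificity 0.95 and 0.98.
- CT-positive share: 20 of 187 (the planned minimum), or 20% in 267 patients. The 20% is an upper value, since section 4 says "less than 20% of abdominal CTs obtained in patients with blunt trauma have intra-abdominal injury".
- Assumed: share redosed q = 0.1–0.3; ratio r of disagreement with CT, redosed to non-redosed BEFAST scans, = 0.5–2; one result per patient per exam; no other covariates.

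**3. Overall disagreement with CT.**
- 20 of 187: FAST (20×0.32 + 167×0.05)/187 = 0.0789; BEFAST (20×0.13 + 167×0.02)/187 = 0.0318.
- 20%: FAST 0.2×0.32 + 0.8×0.05 = 0.104; BEFAST 0.2×0.13 + 0.8×0.02 = 0.042.

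**4. Odds ratio for agreement, ignoring clustering.** Non-redosed BEFAST disagreement is dn = d/(1 − q + q·r), where d is overall BEFAST disagreement. The row-coded odds ratio is odds(FAST disagreement)/odds(dn). Example with 20 of 187, q = 0.3, r = 2: dn = 0.0318/1.3 = 0.0244, and the odds ratio is (0.0789/0.9211)/(0.0244/0.9756) = 3.42. Without redosing in the model it is 2.61.

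| r | 20 of 187 | 20% of 267 |
|---|---|---|
| Redosing not in model | 2.61 | 2.65 |
| 1.5–2 | 2.74–3.42 | 2.79–3.48 |
| 1 | 2.61 | 2.65 |
| 0.5 | 2.21–2.48 | 2.23–2.51 |

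**5. A model of the planned type.** Random patient intercept, maximum likelihood on expected cell probabilities, 40-point quadrature, latent FAST–BEFAST correlation 0.3 (assumed). The result depends on where that correlation is applied.

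| | Within CT+ and CT− strata | To pooled disagreement rates |
|---|---|---|
| Without redosing | 3.16–3.38 | 2.90–2.99 |
| Row-coded, r = 1.5–2 | 3.36–4.67 | 3.1–4.0 |
| Row-coded, r = 1 | no shift | no shift |
| Row-coded, r = 0.5 | 2.61–3.17 | 2.4–2.8 |
| Coded per patient | change of at most 0.02 | essentially no change |

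If redosed patients are equally harder on FAST (1.5–2 times the disagreement on both exams, stratum version), the odds ratio is 3.2–3.5 without redosing and 3.3–4.3 with row coding. So the shift remains even when redosing only marks a difficult patient.

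**6. Precision** (stratum version). With r = 1 and row coding, the standard error of the exam-type log odds ratio rises 4–14%: from 0.57 to 0.59–0.65 at 187 patients, and from 0.43 to 0.45–0.49 at 267. With r = 1.5–2 the rise is 6–26%.

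**7. Shift against sampling noise.** The largest shift is ln(4.33/3.16) = 0.31 at 187 patients, or 0.31/0.57 = 0.55 standard errors. At 267 it is ln(4.67/3.36) = 0.33, or 0.33/0.43 = 0.76 standard errors. Both are the corner with 30% redosed and r = 2.

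**The case against.** The best reply is that nothing goes wrong until an analyst picks a particular coding. Per-patient coding would leave the contrast intact, and the plan does not exclude it. This stands: the harm is conditional. It does not remove the point, because a FAST exam has no redose to record, so 0 on FAST rows is a natural coding, and the text leaves it open.

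Second, the plan may already contain the right comparison. The word *also* in the adjustment sentence can mean an unadjusted model followed by an adjusted one. The event count is set for a "sufficient number of positive results for a model with two predictors (i.e. at least 20 positives", which fits the longer covariate list poorly and favours that reading. Raw sensitivities, specificities and McNemar's test do not involve redosing. This limits the scope to the adjusted regression. But the plan does not label which model is primary, and McNemar's test is listed among the alternatives.

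Third, the size is assumed, its direction is unknown, and it stays below one standard error even in the extreme corner. That also stands. However, a shift in what is being estimated does not shrink as the sample grows, and the covariate buys nothing in return: redosing cannot confound a within-patient comparison in which only one exam can be redosed.

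**Conclusion.** The point holds in conditional form. Contrast redosing is part of the test under evaluation and does not belong among the adjusters of the BEFAST–FAST contrast. If coded as it occurs, the adjusted exam-type coefficient estimates non-redosed BEFAST versus FAST. It is too favourable to BEFAST as performed if redosed scans agree less with CT, too unfavourable if they agree more, and unshifted but less precise if redosing is unrelated to accuracy.

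On the assumptions above, the mixed-model odds ratio moves from about 3.2–3.4 to 2.6–4.7 (correlation within CT strata), or from 2.9–3.0 to 2.4–4.0 (pooled). These are illustrations, since the documents report neither how often redosing happens nor how accurate redosed scans are. Section 6 also says "The investigator will note the presence or absence of injury to the liver, kidney, spleen, or pancreas"; rows at organ level would change the standard errors and could change the odds ratios.

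A reader might infer that the trial's primary result is biased in favour of BEFAST. The documents do not support that: the coding is unstated, the direction cannot be known from them, and the unadjusted results are untouched. Nor does the point say anything about whether or when contrast should be redosed.

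The change should be made because it is cheap and settles the meaning of the estimate before analysis; confidence is medium.

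**What to change.** In section 13, Objective 1, delete contrast redosing from the covariate list of any model that estimates the BEFAST–FAST difference, and keep the other covariates as planned. Add a sentence such as: *Contrast redosing is not a covariate in models that estimate the BEFAST–FAST difference. Its frequency, and BEFAST sensitivity and specificity with and without redosing, will be reported descriptively or in a labelled secondary analysis of BEFAST exams only.*

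If redosing is to stay in the model, state its coding and report the BEFAST–FAST contrast standardised over the redosing observed in the trial.

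The cost is wording only; data collection and sample size do not change. The downside is that the role of redosing is described and not modelled within the comparison. Section 13 holds all analyses until the stopping rule is met, so the wording can be settled before any analysis is run.
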